6.9.1. Background Therapy

Background TCS therapy with low-potency and/or moderate-potency TCS (eg, hydrocortisone 2.5% ointment and/or triamcinolone 0.1% cream) may be used on active lesions. Such TCS

therapy may be provided by the sponsor or the investigative sites. For more detail, see Section 7.7.1 in the protocol.

A summary of the reasons initial background therapy is used will be produced, as well as a summary of the proportion of patients with sponsor-provided TCS at each study visit and a summary of other AD therapy for the responder and partial responder mITT population. Also, a summary of time to initial use of AD background therapy postbaseline will be produced for the responder and partial responder mITT population.

The number of days TCS therapy is used for each patient is also collected on the diary device. The diary device is only dispensed up until Week 16 and is redispensed for patients who are eligible for the randomized withdrawal and downtitration substudy for an additional 16 weeks of the substudy. The proportion of time that the patients did not use TCS therapy will be summarized for these visit intervals (ie, from Week 0 to Week 16 for the responder mITT, partial responder mITT, and nonresponder mITT patients provided with low or moderate TCS). For this analysis, the date of the first entry on the diary device will be used to signify the first day of TCS therapy use.

Descriptive statistics for drug accountability of sponsor-provided TCS (topical low and moderate corticosteroids) will also be provided, including the amount utilized (dispensed tube with cap weight minus the weight of the returned tube with cap) throughout the treatment period from Week 0 to Weeks 16, 36, and 52. The total amount utilized in grams for low and moderate potency will be summarized between visits (Week 0 through Week 4, Week 4 through Week 8, Week 8 through Week 16, and so on) as well as throughout the treatment period from Week 0 through Week 52 (Period 1) and Week 52 through 68 (Period 2). The total amount utilized will also be presented for the aforementioned visit intervals, irrespective of potency. Analyses will be summarized for the responder mITT, partial responder mITT, and nonresponder mITT populations for Period 1. Additionally a summary of total amount used will be provided for the first 16 Weeks of Period 2 by treatment group for those that entered the randomized withdrawal and downtitration studies.

The dispensed weight of sponsor-provided TCS full tubes used for background therapy for the 2 different potencies (low and moderate) varies between countries due to different supply regions. Average weights of full tubes were used to determine the dispensed weights for each region. Returned tubes were weighed with cap (without the carton) to determine the amount of TCS in grams (g) used between visits. For low and moderate potency TCS, the dispensed tube weight with cap (without the carton) in Japan is 13.5 g. For countries supplied by European distributors (Austria, Czech Republic, Denmark, France, Germany, Hungary, Italy, Poland, Spain, and Switzerland), the dispensed weight of low potency TCS is 21 g and moderate potency TCS is 38 g. The remaining countries, supplied by US distributors (Argentina, Australia, India, Israel, Korea, Mexico, Russia, and Taiwan), the weight of low and moderate potency TCS is 40 g.

If a returned tube is not weighed in grams or the tube is not returned then the tube can be classified as partially used, fully used, unused, or unknown. Partially used TCS medication tubes will be considered to be 50% used whereas fully used and unused tubes will be considered as

100% and 0% used, respectively. When drug accountability is not performed for a particular tube of TCS medication or an answer of unknown is given for a tube which is not returned, that particular tube will not be included in the analysis.

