**Figure JAHN.1. Illustration of study design for Clinical Protocol I4V-MC-JAHN.**

#### 4.3.1.1. Screening Period

The duration of the screening period for patients enrolled in JAHN(7) is between 8 and 35 days prior to Visit 1 (Week 0). At Visit 0, the patient will sign the informed consent form (ICF) prior to any study assessments, examinations, or procedures being performed. All screening procedures will be performed according to the Schedule of Activities ([Attachment 1](#)).

Patients who receive a purified protein derivative (PPD) skin test at Visit 0 will need to return within 48 to 72 hours later to read the skin test. Prior to enrollment, treatments for AD will be washed out: 4 weeks for systemic treatments and 2 weeks for topical treatments (not including emollients). Patients will be required to use emollients daily during the 14 days preceding enrollment and throughout the study. If patients have been using emollients daily at the time of screening, then those cumulative days can be utilized to meet inclusion criterion [8]. Additionally, collection of data through daily diaries will be required throughout the screening period. The baseline for the daily electronic patient reported outcome (ePRO) will be the average score of the 7 days prior to enrollment; thus, the minimum screening window was set at 8 days.

All patients who have not previously received the herpes zoster vaccine by screening will be encouraged (per local guidelines) to do so prior to enrollment. Refer to the exclusion criterion [26] for additional information regarding herpes zoster vaccination.

Patients who meet all of the inclusion and none of the exclusion criteria for this addendum (Section 4.5) will continue to Visit 1 and follow all study procedures described in the Schedule of Activities ([Attachment 1](#)) and Section 9 of the main protocol.

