##### *Treatment Period 1: Weeks 0 to 52*

At Visit 1 (Week 0, baseline), study eligibility for each patient will be reviewed, based on all inclusion and exclusion criteria (Section 4.5), and laboratory test results. Patients who meet all criteria will proceed to enrollment and begin the 52-week open-label, treatment period. All activities starting at Visit 2 are identical for patients enrolled in JAHN(7) and patients enrolled in the main protocol.

All patients will be assigned to open label baricitinib 2-mg once daily at Visit 1 (Week 0). All patients will be required to use emollients daily. Topical corticosteroids can be initiated at investigator's discretion during treatment to control worsening and unacceptable symptoms of AD; however, since treatment is open-label it is strongly encouraged not to dispense topical corticosteroids (TCS) until at least 1 week after baricitinib treatment has been started, and only if the patient requires TCS therapy. If possible, monotherapy treatment with baricitinib is preferred if tolerated. Initiation of TCS may occur at either a scheduled or unscheduled visit and investigators should make every attempt to conduct disease severity and safety assessments immediately before administering initial treatment with TCS or other topical/systemic AD

treatments. For management of TCS and other topical therapies, follow the guidelines in Section 7.7.1 of the main protocol.

*Treatment Period 2: Weeks 52 to 104*

At Week 52, all patients participating in JAHN(7) may be eligible to participate in the randomized withdrawal and down-titration substudy as described in Section 5.1.3.1 of the main protocol. To be eligible, a patient in JAHN(7) must meet all of the following criteria:

- Investigator's Global Assessment (IGA) 0, 1, or 2 at Week 52
- has not used high-potency TCS in the last 14 days (potency classification in Appendix 6 of the main protocol)
- does not currently have study drug interrupted

Patients participating in JAHN(7) who are not eligible for the substudy will continue to receive open-label baricitinib 2-mg. Topical corticosteroids can be initiated at investigator's discretion during treatment to control worsening and unacceptable symptoms of AD. For management of TCS, follow the guidelines in Section 7.7.1 of the main protocol.

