4.3. Exploratory Objectives

The exploratory objectives may include evaluating the response to baricitinib treatment regimens on clinical measures and patient-reported outcomes (PROs).

These endpoints may include dichotomous endpoints or change from baseline for the following measures: IGA, Eczema Area and Severity Index (EASI), SCORing Atopic Dermatitis (SCORAD), Patient-Oriented Eczema Measure (POEM), Dermatology Life Quality Index (DLQI), Work Productivity and Activity Impairment (WPAI-AD), European Quality of Life–5 Dimensions–5 Levels (EQ-5D-5L), Itch Numeric Rating Scale (NRS), Atopic Dermatitis Sleep Scale (ADSS) Item 2 score, Skin Pain NRS, and Patient Global Impression of Severity (PGI-S-AD).

Additionally, assessment of background topical corticosteroids (TCS), such as the weight of sponsor-provided TCS and number of days not using TCS, will be analyzed. Patients continuing on placebo as responders will be assessed during the long-term extension for relevant efficacy endpoints.

Time to 4-point itch reduction during the first 14 days after initiation of treatment will be assessed.

Summary of IGA response (0,1) at Week 16 for the proportion of nonresponders with originating study treatment assignment in placebo, baricitinib 1 mg, or baricitinib 2 mg with IGA response (3,4) at the start of study JAHN (Week 0) will be provided.

For IGA (0,1), EASI75, and Itch NRS ≥ 4 -point improvement, a pooled response descriptive summary for baricitinib 2 mg to baricitinib 2 mg and baricitinib 4 mg to baricitinib 4 mg will be done for Week 0 through Week 52 based on I4V-MC-JAHL (JAHL)/I4V-MC-JAHM (JAHM), I4V-MC-JAIY (JAIY), and open label, respectively.

For all the randomized patients who have not entered into the substudy and received at least 1 dose in Period 2, the exploratory analyses will be assessed on the following endpoints: EASI change percent change from baseline, DLQI, SCORAD, POEM, Hospital Anxiety and Depression Scale (HADS). Open-label patients who were not entered into substudy and received at least 1 dose in Period 2 will be analyzed separately in a similar way.

In addition, for the Long-term Baricitinib 4-mg population, the following endpoints, IGA response (0,1), EASI, DLQI, SCORAD, and subjective characteristics of SCORAD (pruritus and sleep loss), will be analyzed in a descriptive way for Week 52 through 104 based on pooled patients, as well as by monotherapy and combination therapy study respectively.

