- Prior use of Cyclosporine (yes, no)
- Reasons Cyclosporine was not used
- Prior use of topical calcineurin inhibitor (TCNI) (yes, no)
- Reasons TCNI was not used

APP.1.2.9.3. Historical Illness and Pre-existing Conditions

Historical illnesses are defined as those conditions recorded in the Pre-existing Conditions and Medical History electronic case report form (eCRF) or from the Prespecified Medical History: Comorbidities eCRF with an end date prior to the informed consent date. The number and percentage of patients with selected historical diagnoses will be summarized by treatment group using the ITT population. Historical diagnoses will be categorized using the Medical Dictionary for Regulatory Activities (MedDRA[®], most current available version) algorithmic standardized MedDRA queries or similar pre-defined lists of preferred terms of interest.

Pre-existing conditions are defined in Section 6.8.3 and will be summarized using the ITT population.

APP.1.2.10. Treatment Compliance

Patient compliance with study medication will be assessed from Week 0 (Visit 2) to Week 104 (Visit 16) or ETV using the ITT population.

All patients are expected to take 1 tablet daily from a bottle for Treatment Period 1 as described in APP.1.2.2. Each bottle contains 36 tablets.

Refer to Section 6.9 for further details on compliance. Analyses will be presented for the ITT population.

APP.1.2.10.1. Background Therapy

Analyses will be presented as described in Section 6.9.1 using the ITT population.

APP.1.2.11. Previous and Concomitant Therapy

Summaries of previous and concomitant medications will be based on the ITT population.

At screening, previous and current AD treatments are recorded for each patient. A summary of previous medications used for AD, including zoster immunization and tuberculosis vaccine and medications that are discontinued after screening and before the first dose of study drug, will be prepared using frequency counts and percentages by preferred medication name, with preferred medication names sorted by frequency. Concomitant therapy will be recorded at each visit and will be classified similarly. An additional summary for previous medications used for AD will be created containing the reason of discontinuation.

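### TCS-free time in Weeks 0 to 16 is summarised only in patients provided with TCS, which leaves out never-provided patients and can distort the descriptive 4-mg versus 2-mg contrast in randomised nonresponders

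*SAP*

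**What the plan says.** SAP Section 4.3 lists TCS use among the exploratory objectives: the weight of sponsor-provided TCS and the "number of days not using TCS, will be analyzed".

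Section 6.9.1 gives the data source: "The number of days TCS therapy is used for each patient is also collected on the diary device". It then defines the summary: "The proportion of time that the patients did not use TCS therapy will be summarized for these visit intervals", namely Week 0 to Week 16, "for the responder mITT, partial responder mITT, and nonresponder mITT patients provided with low or moderate TCS". It adds that "the date of the first entry on the diary device will be used to signify the first day of TCS therapy use". No rule says how a patient who was never provided with TCS is counted, and no time window is set for being provided.

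Note a to Figure JAHN.5.1 in the SAP allows background TCS to be started or restarted at any point in the study. Section 5.2 randomises nonresponders who were not already on 4 mg in a 1:1 ratio to 2 mg or 4 mg, and Section 6.2.3 names the resulting 4-mg versus 2-mg comparisons for Period 1. No test is specified for TCS-free time.

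For the open-label addendum, SAP Appendix 1 (APP.1.2.10.1) states: "Analyses will be presented as described in Section 6.9.1 using the ITT population".

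**The concern.** Being provided with TCS can happen after randomisation and can follow from how well the assigned dose works. Restricting the summary to those patients conditions on something that treatment may affect, so in the nonresponders the two randomised arms are no longer compared on like groups. The patients removed include those with the most favourable outcome, no TCS use at all.

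The stake is interpretation. Under SAP Section 6.4, nonresponders' efficacy data are censored only after permanent discontinuation of study drug. Starting TCS is not listed as an intercurrent event, so an IGA or EASI response reached with added TCS counts as a response. The TCS summaries are therefore a natural place to look when judging how much of a response, or of a dose difference, could be due to TCS.

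**Working it through.** **Inputs.** The documents give no provision rate, no TCS-free share and no expected TCS-sparing effect, so there is no plan figure to reproduce. All values below are assumptions, chosen to span near-universal to moderate provision.

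- r2, r4: share of the 2-mg and 4-mg nonresponders provided with TCS.
- f2, f4: mean TCS-free share among those provided.
- Never-provided patients are taken to use no TCS, so they are 100% TCS-free.

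**Formulae.**

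- The planned summary reports f in each arm, so its contrast is f4 − f2.
- Over all patients, each arm is (1 − r) + r·f, so the contrast is r2(1 − f2) − r4(1 − f4).
- Within an arm, the planned summary falls short of the all-patient value by (1 − r) + r·f − f = (1 − r)(1 − f). This is zero if everyone is provided with TCS (or if those provided never use it), and positive otherwise.

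**Within-arm shortfall at f = 50%.** r = 100%: 0 points. r = 90%: 0.10 × 0.50 = 5 points. r = 80%: 0.20 × 0.50 = 10 points. r = 60%: 0.40 × 0.50 = 20 points.

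**Contrast, 4 mg minus 2 mg, in percentage points.**

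| r2 / r4 | f2 / f4 | Planned | All-patient values, 2 mg / 4 mg | All-patient contrast |
|---|---|---|---|---|
| 100% / 100% | 50% / 60% | +10 | 50% / 60% | +10 |
| 90% / 90% | 50% / 60% | +10 | 55% / 64% | +9 |
| 70% / 70% | 50% / 60% | +10 | 65% / 72% | +7 |
| 80% / 60% | 50% / 60% | +10 | 60% / 76% | +16 |
| 90% / 80% | 50% / 50% | 0 | 55% / 60% | +5 |
| 80% / 60% | 50% / 50% | 0 | 60% / 70% | +10 |
| 90% / 80% | 50% / 45% | −5 | 55% / 56% | +1 |
| 80% / 60% | 50% / 45% | −5 | 60% / 67% | +7 |

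Worked example, sixth row: 2 mg is 0.20 + 0.80 × 0.50 = 0.60; 4 mg is 0.40 + 0.60 × 0.50 = 0.70; difference 0.10. In the last row, 4 mg is 0.40 + 0.60 × 0.45 = 0.67, against a planned difference of 0.45 − 0.50 = −0.05.

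With universal provision the two summaries agree. With equal but incomplete provision, the planned contrast is somewhat too large in these rows. With unequal provision it can be too small, vanish or change sign.

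**Do other planned outputs fill the gap?**

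- Grams of TCS (Section 6.9.1) cover the full nonresponder mITT population in Period 1. They concern sponsor-provided TCS only, although sites may also provide it, and the section does not say whether a patient with no tube counts as zero grams or as missing.
- Time to first background therapy is planned for responders and partial responders only.
- The summary of patients with sponsor-provided TCS at each visit may carry the same limit; the sentence can be read either way.
- Concomitant AD medication (Section 6.10) is summarised in the mITT population, but this is not a measure of TCS-free time.

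For the randomised nonresponders there is thus no clearly stated summary of how many were provided with TCS, which is what a reader would need to interpret a users-only figure.

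**The case against.** **Provision may be near universal.** Nonresponders (Section 5.1) have an IGA of 3 or more or were rescued in the originating study, and the SAP figure note links TCS provision to IGA reaching 3. Provision could also have happened at Week 0, before dose could influence it. A reader might infer that the contrast is distorted by selection after baseline. The documents do not support that: they give no provision window and no rates, and main-protocol Section 7.7.1, which governs TCS use, is not among them. This objection limits the point to what can happen. It does not justify the filter, because under universal provision an all-patient summary gives the same answer.

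**The measure is minor.** It is one exploratory, descriptive summary beside grams and concomitant therapy. That stands, and it sets the priority.

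**The addendum.** A reader might infer that never-provided patients are dropped there too, which would matter because the protocol says "If possible, monotherapy treatment with baricitinib is preferred if tolerated". But Appendix 1 specifies the ITT population, meaning all enrolled patients, and does not say that the limit carries over. Period 1 of the addendum also has a single arm, so no randomised contrast is at risk. Only a need for clear wording remains.

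**The first-entry rule.** In the addendum, "collection of data through daily diaries will be required throughout the screening period". A reader might infer that screening days are added as TCS-free days and inflate the proportion. The text does not support this. Section 6.9.1 fixes the interval at Week 0 to Week 16, Section 6.2.2 anchors postbaseline diary windows on the first dose (Day 1), and the first entry could mean the first TCS entry. The wording is unclear, but no inflation follows from it.

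**Coding every never-provided patient as 100% TCS-free could misclassify.** Someone using only high-potency TCS, or TCS from another source, would be counted as TCS-free. That stands and shapes the fix.

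**Conclusion.** The point holds in limited form. The restriction to provided patients is explicit, the diary data would allow an all-patient summary, and the restriction conditions a by-arm description on a variable that the assigned dose can affect. Where some patients are never provided with TCS and use none, the planned figure understates TCS-free time in that arm by (1 − r)(1 − f). If provision also differs between 2 mg and 4 mg, the contrast among randomised nonresponders can shrink, disappear or reverse: in the assumed cases, 0 instead of +5 or +10 points, and −5 instead of +1 or +7.

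These figures are illustrations. The actual size and direction are unknown, and the effect is close to nil if nearly all nonresponders were provided with TCS. No primary or secondary endpoint is affected, and no planned test of TCS-free time is invalidated, because none is specified. This is a low-cost improvement to an exploratory summary.

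**What to change.** Amend the summary in SAP Section 6.9.1, or record the change in the supplemental SAP that Section 6.18 allows:

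1. Summarise TCS-free time from diary-recorded use in all mITT patients by treatment group, separately for responders, partial responders and nonresponders.
2. Count a patient as 100% TCS-free over the diary-observed Week 0 to 16 days only if no TCS use of any potency or source is recorded. State how missing diary days are handled.
3. Report the share provided with TCS in each arm, explicitly including the nonresponders, and state whether patients with no tube count as zero grams.
4. Keep the users-only summary as supportive.
5. Replace the first-diary-entry wording with an interval that starts at the first JAHN dose (Day 1). This is a clarification only.
6. In APP.1.2.10.1, state that the ITT population means all enrolled patients, without the limit to those provided with TCS.

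The cost is SAP wording and a re-run of one summary from dispensing, diary and concomitant-medication data already collected. The distribution will have a spike at 100%, so show the median and categories beside the mean. The SAP revision history says that data up to Week 104 are already locked, so the new summary must be labelled as added after lock.

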**Attachment 1. I4V-MC-JAHN(7) Schedule of Activities**

|  | Screening Period | Treatment Period 1 |    |    |    |    |    |    | Treatment Period 2 |                |                |                |                |    |    |     | PTFU Period    |                        |
|--|------------------|--------------------|----|----|----|----|----|----|--------------------|----------------|----------------|----------------|----------------|----|----|-----|----------------|------------------------|
| Visit number   | 0                | 1                  | 2  | 3  | 4  | 5  | 6  | 7  | 8                  | 9              | 10             | 11             | 12             | 13 | 14 | 15  | 16/ET          | 801 a       |
| Weeks from entry into JAHN                           | 0                | 4                  | 8  | 16 | 24 | 36 | 48 | 52 | 56                 | 60             | 64             | 68             | 76             | 84 | 92 | 104 | 108            |                        |
| Visit tolerance interval (days) from entry into JAHN | -8 to -35        |                    | ±4 | ±4 | ±4 | ±4 | ±4 | ±4 | ±4                 | ±4             | ±4             | ±4             | ±4             | ±4 | ±4 | ±4  | ±4             | 28 ± 4 after last dose |
| Procedures   |                  |                    |    |    |    |    |    |    |                    |                |                |                |                |    |    |     |                |                        |
| Inclusion and exclusion review                       | X                | X                  |    |    |    |    |    |    |                    |                |                |                |                |    |    |     |                |                        |
| Informed consent                                     | X                |                    |    |    |    |    |    |    |                    |                |                |                |                |    |    |     |                |                        |
| Clinical Assessments                                 |                  |                    |    |    |    |    |    |    |                    |                |                |                |                |    |    |     |                |                        |

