- EASI change and percent change from baseline assessed at Weeks 0 to 48 based on observed data.

- Summary of sponsor provided TCS background therapy weight (g) by potency for weeks 0 to 52.

For the substudy the following analyses/summaries will be provided:

- Proportion of patients achieving IGA (0,1) and IGA (0,1,2) assessed at Weeks 52 to 68.
- Proportion of patients achieving EASI50, EASI75, and EASI90 assessed at Weeks 52 to 68.
- EASI change from baseline and percent change from baseline (mLOCF) assessed at Weeks 52 to 68; Week 0 used as baseline.
- EASI change from baseline and percent change from baseline (mLOCF) assessed at Weeks 52 to 68; Week 52 used as baseline.
- Proportions of patients achieving a ≥ 4 -point improvement assessed at Weeks 52 to 68.
- Itch NRS change from baseline and percent change from baseline (mLOCF) assessed at Weeks 52 to 68; Week 0 used as baseline.
- Itch NRS change from baseline and percent change from baseline (mLOCF) assessed at Weeks 52 to 68; Week 52 used as baseline.

Signature Page for VV-CLIN-127789 v1.0

Approval	PPD 25-Aug-2023 13:26:21 GMT+0000
----------	--------------------------------------

Signature Page for VV-CLIN-127789 v1.0

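### TCS use is summarised in raw grams with no time denominator, so Period 1 interval rows follow the visit schedule and the Week 0–52 mean may fall with dropout

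*SAP*

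**What the plan says.** SAP Section 6.9.1 measures the amount of TCS used by tube weight: "dispensed tube with cap weight minus the weight of the returned tube with cap". These grams are reported in three ways:

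- cumulatively from Week 0 to Weeks 16, 36 and 52;
- by visit interval: the grams "will be summarized between visits (Week 0 through Week 4, Week 4 through Week 8, Week 8 through Week 16, and so on";
- by period: "as well as throughout the treatment period from Week 0 through Week 52 (Period 1) and Week 52 through 68 (Period 2".

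Results are given by potency and irrespective of potency. Period 1 uses the responder, partial responder and nonresponder mITT populations. SAP Section 6.2.1 defines mITT as randomised patients with at least one dose. For the open-label addendum, SAP APP.1.2.10.1 applies the same analyses to the ITT population, meaning all enrolled patients.

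Section 6.9.1 has rules for tubes that are unweighed, unreturned or of unknown status. It has no rule for a patient who leaves part-way through an interval or before Week 52.

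The visit schedule is in Protocol Attachment 1. The row "Weeks from entry into JAHN" runs from Week 0 through 4 and then "8 | 16 | 24 | 36 | 48 | 52 | 56". Protocol Section 4.3.1 says that assessments after screening follow the same time points as the main study.

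Section 6.9.1 also plans other TCS summaries: reasons for initial use, the proportion of patients with sponsor-provided TCS at each visit, time to initial use (responders and partial responders), and the diary-based proportion of time without TCS.

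**The concern.** A total in grams combines how intensively a patient uses TCS with how long that patient was observed. When rows cover different lengths of time, or patients have different follow-up, the total moves even if weekly use does not.

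TCS may be started at the investigator's discretion (Protocol Sections 4.3.1 and 4.3.1.2), and starting background TCS is not itself listed among the intercurrent events in SAP Section 6.4. A patient using TCS can therefore still count as a responder. The TCS summaries are how a reader judges how much topical treatment accompanies the response. SAP Section 4.3 names TCS weight as an exploratory assessment. For Weeks 16–52, grams are the only planned measure of amount, because the diary is not in use for most of that time.

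**Working it through.** The documents give no figure for grams used, so there is no stated result to reproduce. Weekly use is set at a constant 1 g as an assumed scale; the ratios and percentages below do not depend on it.

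**1. Interval rows.** Visit weeks are 0, 4, 8, 16, 24, 36, 48 and 52 (Protocol Attachment 1). Interval grams = weekly rate × interval length.

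| Interval (weeks) | Length (weeks) | Raw grams at 1 g/week | Grams per week |
|---|---|---|---|
| 0–4 | 4 | 4 | 1 |
| 4–8 | 4 | 4 | 1 |
| 8–16 | 8 | 8 | 1 |
| 16–24 | 8 | 8 | 1 |
| 24–36 | 12 | 12 | 1 |
| 36–48 | 12 | 12 | 1 |
| 48–52 | 4 | 4 | 1 |

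The largest row is 12/4 = 3 times the smallest. Use appears to fall by two thirds from Weeks 36–48 to Weeks 48–52 with no change in behaviour. At 10 g/week the rows read 40, 40, 80, 80, 120, 120 and 40 g.

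**2. Visit windows.** Attachment 1 allows ±4 days at each post-baseline visit. Two such visits nominally 28 days apart can be 28 − 8 = 20 to 28 + 8 = 36 days apart, a ratio of 1.8. This is a reason to use actual days rather than nominal weeks.

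**3. Week 0–52 total under dropout.** Let c be the proportion completing Week 52. If discontinuers contribute the grams used before they leave:

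mean total = rate × [c × 52 + (1 − c) × mean week of leaving].

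The only completion figure is 80%, in Protocol Section 4.8.1, for the addendum. It agrees with that document's other planning numbers: 250 × 0.80 × 0.30 = 60, the substudy estimate in Protocol Section 4.4. A completer uses 52 g. With c = 0.80:

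- uniform dropout (mean Week 26): 0.8 × 52 + 0.2 × 26 = 46.8 g, 10.0% low;
- constant hazard: 46.6 g, 10.4% low;
- all leave at Week 4: 0.8 × 52 + 0.2 × 4 = 42.4 g, 18.5% low;
- all leave at Week 48: 0.8 × 52 + 0.2 × 48 = 51.2 g, 1.5% low.

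No completion rate is given for the main study. Over an assumed range with uniform dropout, 90%, 70% and 60% completion give totals 5%, 15% and 20% low.

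**4. Two groups with different dropout.** This is an illustration only; both rates are assumed. At 90% completion the mean is 0.9 × 52 + 0.1 × 26 = 49.4 g. At 70% it is 0.7 × 52 + 0.3 × 26 = 44.2 g. The second is 10.5% lower at identical weekly use.

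**5. With a time denominator.** Dividing by weeks observed returns 1 g/week in every interval and for Weeks 0–52 at any completion rate.

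**The case against.** The best case for leaving the plan alone is that these are drug-accountability summaries. Each row carries its week range, so a reader can see the unequal lengths and divide. Cumulative grams is a legitimate exposure quantity in its own right, and nothing is tested on it. That stands as a limit on importance. It does not supply the per-patient denominator: a reader can divide by nominal weeks but not by actual days or by each patient's follow-up.

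Several stronger readings are tempting, and the documents do not support them.

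- *Interval length biases treatment comparisons.* It does not. Within one interval the nominal length is the same for every group. Substudy visits at Weeks 52, 56, 60, 64 and 68 are all 4 weeks apart, so the randomised comparison over those weeks has no schedule artefact.
- *Period 1 and Period 2 totals cannot be compared.* Section 6.9.1 also plans a Week 0–16 total, which covers the same length of time as Weeks 52–68.
- *Grams are the plan's only measure of TCS use.* The diary proportion of time without TCS is already standardised for time. It counts days rather than grams, however, and covers only Weeks 0–16 and the first 16 substudy weeks.
- *The less effective dose will look as if it needs less TCS.* That requires differential dropout in a known direction, which the documents do not give. The addendum, the source of the 80% figure, has a single arm in Period 1.
- *The SAP counts discontinuers' partial totals as full-period values.* The mITT and ITT populations imply that partial totals are included, but the SAP does not say so. If only Week 52 completers were summarised, the shortfall would not arise.
- *The 4-month update needs correcting.* Appendix 2 lists "Summary of sponsor provided TCS background therapy weight (g) by potency for weeks 0 to 52" without saying whether this is a cumulative total or a by-visit display, and it does not state how many patients had yet to reach Week 52. It governs a lock dated 20 May 2020.

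**Conclusion.** The point holds as a presentation fault in descriptive summaries. The schedule artefact is certain: Period 1 interval rows vary by a factor of 3 at constant weekly use, which distorts the trend over time only. The dropout artefact is conditional on partial totals being counted. If they are, the Week 0–52 mean is about 10% low at 80% completion with uniform dropout, and about 1.5% to 18.5% low depending on timing. All of these figures assume constant weekly use, and 80% is the addendum's planning figure. A spurious difference between groups would follow from unequal dropout, but neither its size nor its direction can be derived from the documents. No primary or secondary endpoint is affected. The change is still worth making because it costs little and grams are the only planned measure of TCS amount for Weeks 16–52.

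**What to change.** In SAP Section 6.9.1, which also governs the addendum through APP.1.2.10.1:

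- For each interval, add grams per week: interval grams divided by the actual days between the dispensing and return visits, times 7.
- For each period total, add each patient's grams divided by that patient's weeks on treatment in the period.
- State how patients who leave before the end of an interval or period are counted.
- Show n and person-weeks for every row, and keep the raw grams alongside.

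Section 6.9 already does the equivalent for tablets: its compliance denominator uses actual days less interruptions. The change needs one division in the table programs and a few lines of SAP text. It uses weights and dates already collected, so Period 1 data can be re-summarised. The drawback is noisier rates for patients with very short follow-up, which is why n and person-weeks should be shown. Appendix 2 concerns a past lock and need not be rewritten.
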